5.1.3 Exploratory Endpoints

The exploratory endpoints include:

- Tumor response endpoints based on modified RECIST 1.1 assessments
- Tumor response endpoints for the subjects in the endometrial and renal cell carcinoma analysis sets based on IIR assessments using both irRECIST, modified RECIST 1.1 and RECIST 1.1.
- To identify and explore blood and tumor biomarkers which correlate with clinical endpoints of this study including safety and efficacy.

5.2 Study Subjects

5.2.1 Definitions of Analysis Sets

The following analysis sets will be defined:

Safety Analysis Set will include all subjects who received any amount of study drug. This will be the analysis set for all safety evaluations.

Full Analysis Set (Intent-to-Treat [ITT] Analysis Set) will include all subjects who entered the study treatment period. Efficacy analyses will primarily be based on the Full Analysis Set. Efficacy analysis will use FAS and the specific cohort analysis set for EC, RCC and other cohorts.

Endometrial Carcinoma Analysis Set will include all endometrial carcinoma subjects from Phase 1b and Phase 2.

Renal Cell Carcinoma Analysis Set will include all renal cell carcinoma subjects from Phase 1b and Phase 2.

Non-Small Cell Lung Cancer Analysis Set will include all non-small cell lung cancer subjects from Phase 1b and Phase 2.

Melanoma Analysis Set will include all melanoma subjects from Phase 1b and Phase 2.

Pharmacokinetic (PK) Analysis Set will include all subjects who have received at least one dose of lenvatinib and have evaluable lenvatinib concentration data.

Pharmacodynamic (PD) Analysis Set will include all subjects who have received at least 1 dose of study drug (lenvatinib or pembrolizumab) and have evaluable pharmacodynamic data.

MTD Analysis Set will include all subjects who have completed cycle 1 treatment of Phase 1b or discontinued early due to DLT. This will be the analysis set to determine MTD.

5.2.2 Subject Disposition

The number and percent of enrolled and treated subjects who were on treatment, and those who discontinued study treatment at the time of the data cut-off will be summarized. The subjects who discontinued study treatment will be tabulated according to the primary reason for discontinuation. The end of study status (e.g., alive, death, withdrew consent, or lost to follow-up) at the data cutoff will also be summarized using the data from the survival follow-up eCRF.

5.2.3 Protocol Deviations

All protocol deviations will be determined prior to database lock and will be agreed upon by a review of individual subject data. This review will be undertaken in collaboration between the Study Director, the Study Statistician, the Study Data Manager and the Study Clinical Operations Manager.

5.2.4 Demographic and Other Baseline Characteristics

The demographics and baseline characteristics, including disease history and prior therapy, will be summarized using descriptive statistics.

- Demographic and other baseline characteristics will be summarized using the Full Analysis Set. For continuous demographic/baseline variables including age (year), height (cm), weight (kg) and BMI (body mass index) (kg/m^2), results will be summarized and presented as n, mean, standard deviation, median, 25% percentile (Q1), 75% percentile (Q3), minimum and maximum values. For categorical variables, the number and percentage of subjects will be used. Categorical variables include age group (<65 years, ≥ 65 years), gender, race (White, Black or African American, Japanese, Chinese, Other Asian, American Indian or Alaska Native, Native Hawaiian or other Pacific Islander, and Other), ethnicity (Hispanic or Latino, not Hispanic or Latino), ECOG performance status, and NYHA cardiac disease classification.

Previous anticancer therapies/medications will be summarized as follows:

- Number of prior regimen,
- Duration of last therapy,
- Best response of last anti-cancer therapy (complete response (CR), partial response (PR), stable disease (SD), progressive disease (PD), not evaluable (NE), not applicable (NA), unknown),
- Time from end of last therapy to first dose,
- Type of last prior therapy (adjuvant, neoadjuvant, metastatic, locally advanced, and unknown),
- Prior surgical procedure (yes, no),

- Time from last prior surgical procedure to first dose,
- Subjects with any prior radiotherapy,
- Radiotherapy site (lymph node [neck/thoracic/abdominal and pelvic/other], bone [skull/spine/thorax/pelvis/extremities], brain, visceral [colorectal mass, lung mass, liver mass, chest, abdomen/pelvis], skin [trunk, extremity, head and neck], musculoskeletal [soft tissue-trunk, extremity, head and neck], miscellaneous),
- Tumor lesion at the site progressed since radiotherapy (yes, no, not evaluated),
- Time from last radiotherapy to the first dose.

Other baseline and disease characteristics include:

- Programmed Cell Death Protein – Ligand 1 (PD-L1) status.
For subjects with both screening and baseline PD-L1 assessments, PD-L1 Status (Pre-treatment) is based on the most recent biopsy (baseline) assessment. PD-L1 positive is determined using a provisional cutoff by IHC per an investigational version of the PD-L1 IHC 22C3 pharmDx (Agilent, Carpinteria, CA, USA).
- FIGO (Fédération Internationale de Gynécologie Obstétrique) grade for endometrial carcinoma subjects.
- Histologic subtype
- Microsatellite instability (MSI) and/or DNA Mismatch Repair (MMR) will be assessed locally and/or centrally for endometrial carcinoma subjects. Overall MSI/MMR Status will be determined by taking the central assessment first if both central and local assessments were available, then taking MMR result if both MMR and MSI assessments were available.
- Karnofsky performance status (KPS) will be summarized for the renal cell carcinoma subjects.

Disease history and characteristics at study entry will include:

- Time since solid tumor diagnosis to date of the first dose (months),
- Tumor type (Non-small cell lung cancer, Renal cell carcinoma, Endometrial cancer, Urothelial cancer, Squamous cell carcinoma of the head and neck, Melanoma),

- Age at diagnosis (in years) summarized both as a continuous and categorical variable (<65, >=65),
- Pathological Tumor-node-metastasis (TNM) staging at diagnosis,
- Target lesions (lymph node [yes/no], non-lymph node [yes/no], and non-target lesions [yes/no] based on the measurable disease criteria at study entry.
- The known mutation status including EGFR, KRAS, NRAS, BRAF, ALK translocation, RET translocation, ROS1 translocation, c-MET, IDH-1, IDH-2, Ki-67, P53, PIK3CA and others.

A summary table and a subject data listing of medical history will be provided, including system organ class and preferred term; current medical condition; date of diagnosis, surgical procedure, or onset of symptoms; and end date/on-going.

5.2.5 Prior and Concomitant Therapy

All investigator terms for medications recorded on the CRF will be coded using the World Health Organization (WHO, Geneva, Switzerland) Drug Dictionary using the March 2016 version or later. The number (percent) of subjects who have taken prior and concomitant medications will be summarized on the Full Analysis Set, by Anatomical Therapeutic Chemical (ATC) Classification and WHO drug preferred term. Prior medications will be defined as medications that stopped prior to the first dose of study drug. Concomitant medications will be defined as medications that (1) have started before the first dose of study drug and are continuing at the time of the first dose of study drug, or (2) have started on or after the date of the first dose of study drug up to 30 days following the last dose of study drug. A medication that cannot be determined as prior/concomitant/post-treatment due to missing/incomplete dates will be regarded as a concomitant medication. The summary of concomitant, including anti-hypertensive, anti-diarrheal and corticosteroid medications/therapies will be provided.

Prior anti-cancer therapies including anti-cancer medications, anti-cancer procedures and radiotherapy will be summarized and listed. Data listings will be provided for all prior and concomitant medications.

5.3 Data Analysis General Considerations

5.3.1 Pooling of Centers

Subjects from all centers will be pooled for all analyses in Phase 1b and Phase 2. Center will not be considered as a factor in the analysis.

5.3.2 Adjustments for Covariates

Not applicable.

5.3.3 Multiple Comparisons/Multiplicity

Not applicable.

5.3.4 Handling of Missing Data, Drop-outs, and Outliers

For incomplete dates involving efficacy and safety data such as adverse events, concomitant medications, laboratory values, vital signs, electrocardiograms (ECGs) and echocardiogram/MUGA data, a conservative imputation will be used for calculation. The imputation rules will be specified in study analysis dataset specification with more details. For endpoints which determine the percentage of responders, patients with unknown response will be treated as non-responders.

5.4 Efficacy Analyses

Tumor response will be assessed by both immune-related RECIST (irRECIST) and modified version of RECIST 1.1 criteria (mRECIST 1.1) per investigator assessment, and by irRECIST, mRECIST 1.1 and RECIST 1.1 per independent imaging review. All efficacy analyses will be performed on the Full Analysis Set for the specific cohort analysis set for EC, RCC and other cohorts. Tabular summary of key features of the efficacy analyses is described in [Appendix 12.5](#) (Summary of Efficacy Analyses). Tumor assessments and overall response to the treatment according to irRECIST are presented in [Appendix 13.1](#).

The best overall response (BOR) is determined once all the data for the subject is known. For this study, a confirmation of complete responses or partial responses is required for both irRECIST and modified RECIST 1.1; and following irRECIST, a confirmation of progression due to a tumor burden is required unless it is per investigator's discretion if the subject was

clinically unstable. The confirmation assessments should be made ≥ 4 weeks later. The BOR is determined by sequentially checking two adjacent assessments with ≥ 4 weeks apart (and with a few special cases). As an example if a subject had a stable disease at the timepoint 1, a partial response at the timepoint 2, a complete response at the timepoint 3, and another complete response at the timepoint 4, then the BOR for this subject is complete response, which was confirmed at the timepoint 4.

To program the BOR per irRECIST: (1) the tumor response data collected via both irRECIST and mRECIST 1.1 CRFs will be used; (2) any further response assessments after the second PD (confirmed PD per irRECIST) identified under irRECIST should not be considered for the BOR determination, however they should be presented in the data listings; (3) all tumor assessments as long as the subjects did not start a new anti-cancer therapy should be considered; (4) if there are more than 1 consecutive missing tumor assessments, all assessments afterward should not be considered for the determination of BOR (also see [Section 5.4.3](#) for PFS). The BOR per irRECIST is defined as follows. [Table 4](#) lists general rules in the derivation of BOR with two consecutive tumor response results (with a few special cases, see Table 4).

- **CR**

To achieve BOR of CR, CR must be observed at two consecutive tumor assessment visits with at least 4 weeks apart before a PD or death (whichever occurs first). If complete responses at two consecutive tumor assessment visits were with less than 4 weeks, the confirmation of CR at the next assessment visit is required.

The documented start date of CR as the BOR is defined as the date of the initial CR that was confirmed at the next consecutive visit (≥ 4 weeks after the initial CR response).

- **PR**

When BOR of CR is not achieved, BOR of PR can be achieved when the initial PR was confirmed by a PR or CR at the next consecutive visit (≥ 4 weeks after the initial PR response). If the two PRs (or PR and then CR) happened at two consecutive tumor assessment visits within 4 weeks, the additional confirmation of the PR is needed.

The documented start date of PR as the BOR is defined as the date of the initial PR that was confirmed at the next consecutive visit (≥ 4 weeks after the initial PR response).

- **PD**

Following irRECIST, subject may continue treatment at the investigator's discretion after the initial PD due to pseudo-progression, if the subject is clinically stable. If a repeating imaging assessment at ≥ 4 weeks after the initial PD was not done, this initial PD response will be considered as a real PD. However, if there was subsequent tumor assessment (≥ 4 weeks) that showed a CR, PR or SD, regularly scheduled imaging assessments should be continued. The BOR will be determined based on all tumor assessments. When a PD is identified and confirmed under irRECIST, any further response assessments after the first PD under irRECIST should not be considered to determine BOR and PFS (i.e. the assessments up to the first PD under irRECIST will be considered for BOR and PFS), however these further assessments should be presented in the data listings.

The documented start date of PD is defined as the date of the initial PD that was confirmed at the next consecutive visit (i.e. a consecutive PD was identified ≥ 4 weeks after the initial PD response), or the date of the initial PD if a repeating imaging assessment was not done, or the date of the first PD identified during irRECIST evaluations.

- **UNK (Unknown)**

If the subject did not have a baseline tumor assessment, then BOR = UNK (Unknown).

- **NE (Not Evaluable)**

If the subject did not have a post-baseline tumor assessment, or the subject only had one post-baseline tumor assessment of an early SD (duration < 5 weeks) as the overall response, or post-baseline tumor assessments are not evaluable (i.e. recorded as 'NE' as overall responses via the CRF, maybe due to missing anatomy or poor image quality), then BOR = NE.

- **SD**

If the BOR is not a confirmed CR/PR, NE, Unknown or PD, then the BOR is stable disease (SD).

Table 4 General Rules Deriving BOR per irRECIST

Timepoint 1 Overall Response	Timepoint 2 (\geq 4 weeks since Timepoint 1) Overall Response	BOR
CR	CR	CR
CR	PR	SD if duration of SD \geq 5 weeks, otherwise PD
CR	SD	SD if duration of SD \geq 5 weeks, otherwise PD
CR	PD	SD if duration of SD \geq 5 weeks, otherwise PD
CR	NE	SD if duration of SD \geq 5 weeks, otherwise NE. In the special case, if CR is at the next timepoint after NE, BOR will be CR.
CR ^a		SD if duration of SD \geq 5 weeks, otherwise NE
PR	CR ^b	PR
PR	PR	PR
PR	SD	SD. In the special case if PR or CR is at the next timepoint after SD, BOR will be PR.
PR	PD	SD if duration of SD \geq 5 weeks, otherwise PD
PR	NE	SD if duration of SD \geq 5 weeks, otherwise NE. In the special case, if PR or CR is at the next timepoint after NE, BOR will be PR.
PR ^a		SD if duration of SD \geq 5 weeks, otherwise NE
SD	CR ^b	SD
SD	PR ^b	SD
SD	SD	SD
SD	PD	SD if duration of SD \geq 5 weeks, otherwise PD
SD	NE	SD if duration of SD \geq 5 weeks, otherwise NE
SD ^a		SD if duration of SD \geq 5 weeks, otherwise NE
PD	CR ^b	SD if duration of SD \geq 5 weeks, otherwise PD
PD	PR ^b	SD if duration of SD \geq 5 weeks, otherwise PD
PD	SD	SD if duration of SD \geq 5 weeks, otherwise PD
PD	PD	PD

PD	NE	PD
PD ^a		PD
NE	NE	NE
UNK	UNK	UNK (Unknown) if there was no a baseline tumor assessment.

^a If this was the only tumor response assessment (e.g. study treatment was discontinued). ^b The subject should be followed for ≥ 4 weeks to confirm the CR/PR.

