1st radiologic evidence of PD	Repeat imaging at ≥ 4 weeks (next TA time point) to confirm PD	May continue study treatment at the Investigator's discretion while awaiting confirmatory scans	Repeat imaging at ≥ 4 weeks to confirm PD per physician discretion only	Discontinue treatment
Subsequent scan confirms PD	No additional imaging required	Discontinue treatment	No additional imaging required	N/A
Subsequent scan shows SD, PR or CR	Continue regularly scheduled imaging assessments	Continue study treatment at the Investigator's discretion	Continue regularly scheduled imaging assessments	May restart study treatment if condition has improved and/or clinically stable per investigator's discretion

CR = complete response, PR = partial response, SD = stable disease, PD = progression disease, N/A = not applicable.

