5.4.4 Exploratory Efficacy Analysis

The efficacy tumor response endpoints (eg, PR, CR, SD and PD) will be explored based on modified RECIST 1.1 and RECIST 1.1 assessments. Same as the irRECIST, (1) a confirmation of complete responses or partial responses is required; (2) all tumor assessments as long as the subjects did not start a new anti-cancer therapy should be considered; (3) if there are more than 1 consecutive missing tumor assessments, all assessments afterward should not be considered for the determination of BOR (also see [Section 5.4.3](#) for PFS). However, different from irRECIST, a pseudoprogression is considered as a PD per the modified RECIST 1.1 and RECIST 1.1. Therefore, following the modified RECIST 1.1 and RECIST 1.1, any further tumor response assessments after the initial PD are not considered to determine BOR. For programming, only the tumor response data collected via the CRF of the modified RECIST 1.1 will be used. The general rules in the derivation of BOR with two consecutive tumor response results following the modified RECIST 1.1 and RECIST 1.1 are described in Table

7.

Table 7 General Rules Deriving BOR per modified RECIST 1.1 and RECIST 1.1

Timepoint 1 Overall Response	Timepoint 2 (\geq 4 weeks since Timepoint 1) Overall Response	BOR
CR	CR	CR
CR	PR	SD if duration of SD \geq 5 weeks, otherwise PD
CR	SD	SD if duration of SD \geq 5 weeks, otherwise PD
CR	PD	SD if duration of SD \geq 5 weeks, otherwise PD
CR	NE	SD if duration of SD \geq 5 weeks, otherwise NE. In the special case, if CR is after NE, BOR will be CR.
CR ^a		SD if duration of SD \geq 5 weeks, otherwise NE
PR	CR ^b	PR
PR	PR	PR
PR	SD	SD. In the special case if PR or CR is after SD, BOR will be PR.
PR	PD	SD if duration of SD \geq 5 weeks, otherwise PD
PR	NE	SD if duration of SD \geq 5 weeks, otherwise NE. In the special case, if PR or CR is after NE, BOR will be PR.
PR ^a		SD if duration of SD \geq 5 weeks, otherwise NE
SD	CR ^b	SD
SD	PR ^b	SD
SD	SD	SD
SD	PD	SD if duration of SD \geq 5 weeks, otherwise PD
SD	NE	SD if duration of SD \geq 5 weeks, otherwise NE
SD ^a		SD if duration of SD \geq 5 weeks, otherwise NE
PD ^c		PD
NE	NE	NE

UNK	UNK	UNK (Unknown) if there was no a baseline tumor assessment.
-----	-----	--

^a If this was the only tumor response assessment (e.g. study treatment was discontinued).

^b The subjects should be followed for ≥ 4 weeks to confirm the CR/PR.

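### SAP 5.4 gives two different cut points for best overall response per irRECIST, and one of them, read literally, discards confirmed responses that follow an unconfirmed PD

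*SAP*

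**What the plan says.** SAP 5.4 has four numbered rules for programming BOR per irRECIST. Rule 2 says that "any further response assessments after the second PD (confirmed PD per irRECIST) identified under irRECIST should not be considered for the BOR determination". The PD bullet in the same section says that once a PD has been identified and confirmed, "any further response assessments after the first PD under irRECIST should not be considered to determine BOR and PFS". It then repeats the point in brackets: "i.e. the assessments up to the first PD under irRECIST will be considered for BOR and PFS". The PFS text in SAP 5.4.3 uses similar first-PD wording.

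Other text in the plan bears on what is meant:

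- Just before the disputed sentence, the PD bullet covers an initial PD followed by CR, PR or SD. Imaging continues and "The BOR will be determined based on all tumor assessments".
- SAP Table 4 has rows for PD then CR and PD then PR. Their footnote b reads "The subject should be followed for ≥ 4 weeks to confirm the CR/PR".
- Protocol 9.5.1.3, Table 6, has a row headed "Subsequent scan shows SD, PR or CR", under which regular imaging goes on.
- SAP 5.4.4 gives the rule for modified RECIST 1.1 and RECIST 1.1, introduced as different from irRECIST: "any further tumor response assessments after the initial PD are not considered to determine BOR".
- The PD bullet offers three dates for the start of PD. One is the initial PD that the next visit confirmed. Another, listed separately, is the first PD found in the irRECIST evaluations.
- The CR bullet requires the confirming pair to come before a PD or death. It does not say whether that PD must be confirmed.

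**The concern.** One derivation has two cut points, and the phrase that separates them is undefined. The PD bullet already has its own words for the opening scan of a confirmed pair, and it lists the first PD as a separate dating option. A programmer could therefore reasonably take the first PD to be the earliest PD on record, confirmed or not.

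On that reading, a subject with an unconfirmed PD, then a confirmed response, then a confirmed PD loses the response. irRECIST is used here so that an unconfirmed PD does not end the assessment, so this result would defeat its purpose. A subject's best response would also depend on later scans: a responder at Week 24 could become a non-responder at data cutoff.

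BOR feeds ORR(Week 24), ORR at cutoff, DCR, CBR and the responder set for DOR. The same wording reaches PFS dating.

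**Working it through.** The plan states no figure on this point, so the check applies each rule to possible scan records.

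**Inputs.** Scheduled scans are at Weeks 6, 12, 18 and 24, then 33, 42, 51 and so on (Protocol Table 9). Response pairs and special cases follow SAP Table 4. Adjacent scans are taken to be at least 4 weeks apart, and a record ends when a PD is confirmed.

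**Records under each cut:**

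| Record | After the confirming PD (rule 2) | At the opening scan of the confirmed pair | At the earliest PD, once any PD is confirmed |
|---|---|---|---|
| PD-PR-PR-PD-PD (Weeks 6, 12, 18, 24, 33) | PR | PR | PD |
| PD-SD-PD-PD (Weeks 6, 12, 18, 24) | SD | SD | PD |
| SD-PD-PR-PR-SD-PD-PD (Weeks 6 to 51) | PR | PR | SD |

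In the second row, SD at Week 12 meets the 5-week minimum, so the PD-then-SD row of Table 4 gives SD.

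**All records.** Every sequence of CR, PR, SD, PD and NE with 2 to 7 scans was enumerated and responder status compared.

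- Confirming PD against the opening scan of the pair: no difference in any sequence. Only the confirming PD lies between the two cuts.
- Confirming PD against the earliest PD: no difference in the 25, 120 and 580 sequences of 2, 3 and 4 scans. The two differ in 3 of 2,800 with five scans, 37 of 13,520 with six and 298 of 65,280 with seven. In every case a response was lost and none was gained. These are counts of possible patterns, not probabilities.

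**Why five scans.** An affected responder needs one unconfirmed PD, at least two scans for a confirmed response and two for a confirmed PD: 1 + 2 + 2 = 5. The fifth scheduled scan is at Week 33. A change in DCR needs only 1 + 1 + 2 = 4 scans, as in the second row.

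**Week 24 against cutoff.** At Week 24 the first record is PD-PR-PR-PD. No PD is yet confirmed, so the subject is a responder under either rule. When Week 33 confirms the PD, the earliest-PD reading makes the same subject a non-responder at cutoff.

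**Dates.** For the first record, the confirmed PD starts at Week 24. On the earliest-PD reading PFS would be dated at Week 6, which is 24 − 6 = 18 weeks sooner. That contradicts SAP 5.4.3, which defines PFS by confirmed PD. If responders were taken from rule 2 but the PD date from the third dating option, DOR would run from Week 12 to Week 6: 6 − 12 = −6 weeks.

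**Size per lost responder.** 1/120 = 0.8 points, 1/100 = 1 point, 1/20 = 5 points.

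**The case against.** The best defence is that the intent can be recovered from the text. The disputed sentence starts from a confirmed PD: "When a PD is identified and confirmed under irRECIST, any further response assessments after the first PD under irRECIST should not be considered". Beside rule 2, the natural pairing is first PD for the opening scan and second PD for the confirming scan, and those two cuts give identical responder status. It could also mean the first PD recorded in the irRECIST evaluations after an initial PD on the modified RECIST form. That PD would be the second one, and BOR would again match rule 2. The sentence on using all assessments, Table 4 footnote b and the contrast drawn in SAP 5.4.4 all point away from the earliest-PD reading. Detailed derivation rules are kept in separate documents (SAP section 9).

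Most of this stands, and it limits the point to an ambiguity. It does not remove the conflict. The first-PD cut appears twice in the PD bullet and again in 5.4.3, the separate dating option invites the literal reading, and the CR bullet leaves the same gap.

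A reader might infer three stronger things that the documents do not support:

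- *ORR is understated.* That follows from only one reading, and the trigger is a later confirmed PD. An unconfirmed later PD, or a death, leaves the response in place.
- *The primary endpoint is biased.* On the four scheduled scans, ORR(Week 24) responder status does not change. It could change only with an unscheduled scan, or if a PD confirmed after Week 24 were applied backwards.
- *A benchmark would be missed.* Protocol Table 13 shows 35/100 with a lower limit of 0.257, and 34/100 would give 0.248, below 25%. The arithmetic is right, but Table 13 illustrates precision and is not a decision rule.

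**Conclusion.** SAP 5.4 contains conflicting cut points for BOR per irRECIST. One of them, taken literally, gives results that contradict the rest of the section. On that reading confirmed responses after an unconfirmed PD are lost once a later PD is confirmed, some SD becomes PD in DCR, and PFS may be dated at an unconfirmed PD. Any error in ORR is downward and falls mainly on ORR at data cutoff.

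The result depends on which reading is programmed, and on scans being at least 4 weeks apart. The documents give no frequency for the affected records, so only the cost per lost responder can be stated.

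**What to change.** 1. In the PD bullet of SAP 5.4 (both places) and in the PFS text of 5.4.3, replace the first-PD wording with: *the initial PD of the first confirmed PD pair (two consecutive PD assessments at least 4 weeks apart), or the initial PD if no repeat imaging was done*.
2. Align programming rule 2 with that definition.
3. Delete the third PD-date option, or align it with the definition.
4. In the CR bullet, require the pair to come before a confirmed PD as defined above.
5. State that an unconfirmed PD followed by SD, PR or CR does not end the BOR window.
6. Add PD-PR-PR-PD-PD = PR as a worked example beside the existing one.

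The cost is a few sentences in the SAP and one check of the derivation for the few subjects with an unconfirmed PD. No new data or subjects are needed.
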